16.1. General Considerations

Data will be collected and analyzed separately for the placebo-controlled period and LTE period:

1. After the placebo-controlled period is completed, efficacy and safety analyses will be performed.
2. Analyses will be performed as needed during the LTE period. Descriptive statistics will be used to evaluate the long-term safety and efficacy data of BIIB092.

Summary statistics will be presented. For continuous endpoints, summary statistics will generally include: number of participants with data, mean, SD, median, and range. For categorical endpoints, this will generally include: number of participants randomized or dosed, number of participants with data, and the percentage of those with data in each category. Data for participants who were randomized to BIIB092 low dose (125 mg once every 4 weeks or 375 mg once every 12 weeks) will be pooled for statistical testing and modeling for efficacy, PD, and health outcome analyses, unless otherwise specified in the placebo-controlled period. All statistical tests will be 2-sided.

Similar analyses will be applied to both the placebo-controlled and LTE periods, except for efficacy analyses, which will be detailed in the statistical analysis plan (SAP).

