16.4.3. Analysis for the Long-Term Extension Period

The analysis will include all participants who received at least 1 dose of study treatment in the LTE period.

The endpoints for the LTE period are change from baseline over the placebo-controlled and LTE periods of the study. Analyses will be presented by treatment group in the LTE period using the placebo-controlled period baseline. Details of the analyses will be prespecified in the SAP.

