16.7.2. Methods of Analysis

The scores for and changes from baseline in the ZBI and QoL-AD, and cumulative resource utilization collected from the RUD-Lite assessments up to Week 72, will be summarized by treatment group.

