2.2 Exploratory LTE Objectives and Endpoints

- To further evaluate the immunogenicity of BIIB092 after multiple doses in participants with MCI due to AD or with mild AD as measured by the incidence of anti-BIIB092 antibodies in serum over time up to Week 238.
- To further assess the effect of BIIB092 on disease progression as measured by fluid and radiological biomarkers, as well as additional clinical and health outcomes as measured by the following:
 - Changes over the placebo-controlled period and LTE period on the CDR-SB, MMSE, ISLT, Category Fluency and Letter Fluency tests from the DKEFS, DSST, Trails A, eCog, ADCS-ADL, FAQ, ADAS-Cog-13 (13-item), and NPI-10
 - Changes over the placebo-controlled period and LTE period on the ZBI, QoL-AD, and RUD-Lite
 - Changes over the placebo-controlled period and LTE period in CSF and blood biomarkers (for those who consent to participate in the optional CSF sampling substudy)
 - Changes over the placebo-controlled period and LTE period on 18F-MK6240 PET and MRI brain morphometric measures (for those who consent to participate in the optional PET substudy)
- To assess BIIB092 PK in serum (trough serum BIIB092 concentrations) and in CSF (for those who consent to participate in the optional CSF sampling substudy) from the samples collected at the visits indicated in the Schedule of Activities in participants with MCI due to AD or with mild AD.

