5.8 Additional Exploratory Endpoints

5.8.1 Health Outcomes

The FAS will be used for the analysis of health outcomes data for LTE period. The result will be listed by LTE treatment group for placebo-controlled and LTE period.

CONFIDENTIAL

The information contained herein may not be used, disclosed, or published without the written consent of Biogen MA Inc.

6 Appendix I: Visit Window Mapping

For data that are summarized by visit and longitudinal analysis, assessment from all scheduled visits including EOT visit and EOS visit, and all unscheduled visits will be mapped to an appropriate analysis visit using a windowing scheme. Analysis visit windows are defined in [Table 1 - Table 12] for different endpoints.

If there are 2 or more assessments from visits other than EOT or EOS visits mapped to the same analysis visit for a subject, the assessment that is closest to the target visit day will be used for analysis. If there are 2 or more assessments from visits other than EOT or EOS visits mapped to the same analysis visit with the same distance from the target visit day, then select the later one(s) for the analysis. If there are 2 or more assessments from visits other than EOT or EOS visits mapped to the same analysis visit and on the same day, use the average value for quantitative parameters and the worst value for qualitative parameters for analysis.

Table 1. Visit Windows for Efficacy Endpoints

Efficacy Endpoint	Analysis visit	Target visit day	Analysis visit window
CDR, NPI-10, ADAS-Cog13, FAQ, and ADCS-ADL	Baseline	1	Most recent non-missing pre-dose value
	Week 24	169	[2, 267]
	Week 52	365	[268, 456]
	Week 78	547	[457, the end day of the placebo-controlled period ¹]
	Week 104	729	[one day after the start day of the LTE period ² , 813]
	Week 128	897	[814, 981]
	Week 152	1065	[982, 1149]
	Week 176	1233	[1150, 1317]
	Week 200	1401	[1318, 1492]
	Week 226	1582	≥1493
ISLT, DKEFS, DSST, Trails A,	Baseline800-	1	Most recent non-missing pre-dose value
	Week 12	85	[2, 141]
	Week 28	197	[142, 239]
	Week 40	281	[240, 337]
	Week 56	393	[338, 435]
	Week 68	477	[436, 512]
	Week 78	547	[513, the end day of the placebo-controlled period ¹]
	Week 108	757	[one day after the start day of the LTE period ² , 841]

CONFIDENTIAL

The information contained herein may not be used, disclosed, or published without the written consent of Biogen MA Inc.

Efficacy Endpoint	Analysis visit	Target visit day	Analysis visit window
	Week 132	925	[842, 1009]

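### SAP 5.8.1 provides only a listing for the LTE health outcomes (ZBI, QoL-AD, RUD-Lite), where the protocol, read as a whole, calls for summaries by treatment group

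*SAP*

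**What the plan says.** **Endpoint.** Protocol Section 6 and SAP 2.2 both give, among the exploratory LTE endpoints, "Changes over the placebo-controlled period and LTE period on the ZBI, QoL-AD, and RUD-Lite".

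**Protocol analysis.** Section 16.7.2 covers "The scores for and changes from baseline in the ZBI and QoL-AD", together with "cumulative resource utilization collected from the RUD-Lite assessments up to Week 72, will be summarized by treatment group". Section 16.1 states: "Similar analyses will be applied to both the placebo-controlled and LTE periods, except for efficacy analyses".

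**SAP analysis.** Section 5.8.1 has two sentences. The first sets the population: "The FAS will be used for the analysis of health outcomes data for LTE period". The second sets the output: "The result will be listed by LTE treatment group for placebo-controlled and LTE period". Section 3.3 defines four LTE treatment groups, with the two low-dose regimens pooled, for efficacy and health outcome analyses. Section 4.1 leaves health outcomes out of the LTE interim analysis. Section 4.2 runs everything in Section 5 at the final analysis.

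**Data collection.** Protocol Table 1 schedules the three instruments at Screening Visit 3 and Weeks 20, 48 and 68, and at early termination. Tables 2 to 4 add Weeks 124, 172 and 226; the last column also serves early termination.

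**The concern.** A listing shows individual records and estimates nothing. The endpoint is worded as change over two periods, so it needs at least a change score set out by visit and group. SAP 5.8.1 provides none of these. The interim analysis excludes health outcomes, so the final analysis is the only point at which the LTE could report on caregiver burden, quality of life or resource use by group. If the SAP is programmed as written, those data are collected from participants and caregivers and then not summarised.

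**Working it through.** No formula or stated figure is involved, so the check is a comparison of the texts. The only arithmetic is for the proposed visit windows.

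**Step 1: does the protocol's plan reach the LTE?** Section 16.7.2 alone does not settle this. Its only stated time limit, attached to the RUD-Lite, is Week 72, and LTE dosing starts at Week 80. The link is Section 16.1, which applies similar analyses to both periods except for efficacy. Health outcomes are not inside that exception: 16.1 itself names efficacy, PD and health outcome analyses as separate items when it pools the low-dose regimens, and health outcomes have their own Section 16.7. Add the LTE endpoint in Section 6, and a summary by treatment group is what the protocol plans for the LTE.

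**Step 2: what is to be summarised?** For ZBI and QoL-AD, 16.7.2 names scores and changes from baseline. For RUD-Lite it names cumulative resource use.

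**Step 3: does SAP 5.8.1 deliver it?**

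| Item | ZBI | QoL-AD | RUD-Lite |
|---|---|---|---|
| Output in SAP 5.8.1 | listing | listing | listing |
| Group summary specified | no | no | no |
| Visit window in Appendix I, Tables 1 to 16 | no | no | no |

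Three of 3 instruments have a listing as their only output, 0 of 3 have a summary, and 0 of 3 have a window. By contrast, SAP 5.3.4 says that baseline and change scores for the exploratory clinical endpoints are summarised by visit and LTE treatment group.

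**Step 4: could other SAP text supply the summary?** Section 5.1 says what summary tables contain, not which endpoints receive one. Section 3.3 names groups but no statistic. Section 5.2 separates summary tables from listings and describes listings as record-level output with a study-period indicator, presented by LTE treatment group. The 5.8.1 wording matches that description. Section 5.2.1 likewise asks for some items to be both summarised and listed.

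**Step 5: windows.** Appendix I places boundaries at the midpoint between target days. For example, Weeks 24 and 52 give (169 + 365)/2 = 267, which is the printed boundary for the CDR. Using the protocol's study days:

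- Weeks 20 and 48: (141 + 337)/2 = 239
- Weeks 48 and 68: (337 + 477)/2 = 407
- Weeks 124 and 172: (869 + 1205)/2 = 1037
- Weeks 172 and 226: (1205 + 1583)/2 = 1394

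Some Appendix I tables print day 1582 for Week 226. That gives 1393.5, which rounds up to the same boundary.

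**The case against.** **The wording may be loose.** SAP 5.5.1 speaks of listing CSF-to-serum ratios along with descriptive statistics, and 5.7.1 describes a summary table as listing counts and percentages. With 3.3 and 5.1, one could argue that 5.8.1 means a tabulation. This part stands: the intent is not certain. But both of those passages name their statistics, and 5.8.1 names none. Even on the loose reading a programmer could not build the table.

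**The duty is indirect.** Section 16.1 says similar analyses, and it also says LTE analyses are performed as needed. A reader might infer that the protocol expressly requires score-and-change summaries of all three instruments in the LTE. It does not. The duty comes from combining 16.1, 16.7.2 and the Section 6 endpoint, and for RUD-Lite the planned measure is cumulative use.

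**Data may be sparse.** SAP 4.1 expects only a few participants with LTE health-outcome data at the placebo-controlled lock, and 5.6.2 says nobody reached Week 226. The exposure categories in 5.2.4 stop at 26 infusions. With 20 infusions through Week 76 and the 21st at Week 80, the 26th falls at Week 80 + 5 × 4 = 100 if none is missed, which is before Week 124. This is an inference from table categories, but it suggests that few participants may have reached a scheduled LTE health-outcome visit. A reader might assume that Weeks 124 and 172 hold usable data; no passage shows it. Early-termination assessments can still supply LTE data at irregular times. Sparse data could justify a reduced output, but 5.8.1 does not give that reason, whereas 5.6.2 explains why structural MRI was dropped.

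**No comparison was planned.** This stands. Protocol 16.7.2 is descriptive, so the absence of an MMRM or a group test is not a departure.

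**Conclusion.** The point holds: followed literally, SAP 5.8.1 leaves a named LTE endpoint without any group-level summary for its three instruments. This rests on reading *listed* as the SAP uses it in 5.2, and on 16.1 carrying the plan of 16.7.2 into the LTE.

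Three limits apply. First, the gap concerns the LTE; placebo-controlled data may be summarised in the separate SAP, which was not supplied. Second, a reader might count these as the only 3 of 15 named LTE clinical and health-outcome instruments without a summary. That contrast is not supported, because in SAP 5.3.4 the two fluency tests, DSST and Trails A enter only through the EMACC composite. The accurate statement is that ZBI, QoL-AD and RUD-Lite have no summary at all, even within a composite. Third, the endpoints are exploratory, and neither the primary safety analysis nor the CDR-SB analysis is affected. It should be corrected because the remedy is nearly free.

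**What to change.** Replace the second sentence of SAP 5.8.1 with descriptive summaries by visit and LTE treatment group (the four groups of 3.3):

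- ZBI and QoL-AD: score and change from placebo-controlled baseline. This is the baseline SAP 3.4 sets for the combined periods, and it agrees with the protocol's rule for LTE efficacy in 16.4.3: "Analyses will be presented by treatment group in the LTE period using the placebo-controlled period baseline".
- RUD-Lite: cumulative resource use.

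Keep the listing, and show n in every cell so that sparse cells are visible. No MMRM is required.

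Add a window table to Appendix I:

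| Analysis visit | Target day | Window |
|---|---|---|
| Week 20 | 141 | [2, 239] |
| Week 48 | 337 | [240, 407] |
| Week 68 | 477 | [408, end of placebo-controlled period] |
| Week 124 | 869 | [LTE start + 1, 1037] |
| Week 172 | 1205 | [1038, 1394] |
| Week 226 | 1583 | ≥1395 |

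These windows also assign early-termination assessments to a visit. If the sponsor prefers a listing alone because few participants have LTE data, 5.8.1 should say so and record it as a departure from the protocol's plan.

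Cost: SAP wording and a few extra tables, possibly sparse, for exploratory endpoints. No new data are needed.

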- ⁴ Pregnancy testing is required for women of childbearing potential only; for these participants, a serum pregnancy test is to be performed at EOS (or ET) Visits, and a urine pregnancy test is to be performed at every dosing visit.

[REDACTED]

- ⁶ Triplicate 12-lead (paper) ECGs will be obtained at each specified timepoint. ECGs are to be performed in triplicate, with each ECG performed about 1 minute apart and before blood draws on appropriate days. Each ECG must be performed after the participant has been resting (supine) for 10 minutes. ECGs will be read by a central reading facility. Clinical significance of potential ECG abnormalities will be determined by the Investigator.
- ⁷ Vital signs will include SBP, DBP, heart rate, body temperature, and respiratory rate and will be measured with the participant supine and after the participant has been resting for at least 10 minutes. Single vital sign readings will be obtained.
- ⁸ Brain MRI may include, but will not be limited to, the following sequences: 3D T1 weighted, fluid attenuated inversion recovery, T2* weighted, diffusion weighted imaging, and proton density/T2 weighted MRI. For further details on MRI sequences, please see the procedural manual for MRI. During the LTE period, the visit date for the MRI can vary by ± 10 days from the specified visit day.

[REDACTED]

- ¹² It is recommended that postbaseline CDR assessments be conducted at the same time of day at which the baseline assessment was performed to avoid diurnal variation. The rater who conducts the CDR for a participant/informant cannot complete any other rating scales for that same participant/partner or be the study site coordinator and will be blinded to all other study-related data.

CONFIDENTIAL

The information contained herein may not be used, disclosed, or published without the written consent of Biogen MA Inc.

[REDACTED]

¹⁴Participants' tobacco use status will be assessed while collecting information on concomitant therapies.

CONFIDENTIAL

The information contained herein may not be used, disclosed, or published without the written consent of Biogen MA Inc.

Table 4: Schedule of Activities for Week 180 Through Week 238 or Follow-Up Visit of the Long-Term Extension Period

	Long-Term Extension Period														UV for Change in AD Medication ¹
Study Week	180	184	188	192	196	200	204	208	212	216	220	224/ EOT	226/ EOS or ET ²	238/FUV (14 weeks After Last Dose) ³	

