- ² All participants who discontinue study treatment prematurely will be asked to remain in the study and continue all protocol-specified visits and procedures. These participants should be encouraged to attend at least the Week 80, 104, 116, 128, 152, 156, 176, 196, 200, 224, and 226/EOS Visits, depending on when treatment was discontinued, and undergo all the scheduled procedures. At a minimum, these visits should include assessment of AEs/SAEs and concomitant medications and key clinical assessments, including at least the CDR, MMSE, ISLT, ADAS-Cog 13, ADCS-ADL, and FAQ. Participants who discontinue study treatment prematurely will also be asked to return to the study site for a Follow-up Safety Visit 14 weeks after receiving the last dose of study treatment. See Section 10.1 for details. Participants who withdraw from the study prematurely are to return to the study site for an ET Visit and ET assessments. If the withdrawn participant has discontinued treatment within 3 months of the previous primary efficacy assessment (CDR) and no significant changes in cognitive status are suspected by the Investigator, the clinical efficacy assessments specified in the ET Visit are not required; the study site should notify the Sponsor in such cases. An MRI scan should be performed if withdrawal occurs ≥ 6 months after the previous MRI. Blood for biomarker analysis should be collected if the participant withdraws ≥ 4 weeks after the previous sample was collected. [REDACTED] See Section 10.3 for details.
- ³ Participants who discontinue study treatment and withdraw from the study early are to have a Follow-up Safety Visit (FUV) 14 weeks after the final dose. Participants who discontinue study treatment prematurely are to return to the study site for a Follow-up Safety Visit 14 weeks after receiving the last dose of study treatment. See Section 10.1 and Section 10.3 for details.
- ⁴ All participants should be observed and monitored by study staff for a minimum of 1 hour after the end of an infusion. Participants who experience an AE or SAE related to BIIB092 infusion should remain at the site or be sent to an inpatient monitoring facility until the Investigator has determined that the event(s) has resolved or do not require further monitoring at the site or in an inpatient setting.
- ⁵ All assessments and blood collection during dosing days will be performed prior to infusion, unless otherwise specified. Doses should be administered at least 21 days apart.

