Participants who meet the LTE inclusion and exclusion criteria will be eligible to enter the dose-blinded LTE period, which includes the LTE Screening Period of approximately 4 weeks starting at Week 76, the 144-week Treatment Period starting at Week 80, the EOS Visit at Week 226, and the Follow-up Visit at Week 238.

Participants will have approximately 39 outpatient clinic visits during the LTE period:

[figure not shown]
- Participant eligibility will be determined at Week 76 or Week 78 of the placebo-controlled period and confirmed at Week 80 of the LTE period.
- At the Week 80 Visit, eligible participants will have scheduled assessments per the Schedule of Activities and receive the first infusion of BIIB092 during the LTE period. All participants receiving placebo in the placebo-controlled period will receive BIIB092 at the high dose (2000 mg) once every 4 weeks during the LTE period.
- Participants will return to the clinic at 4-week intervals during the Treatment Period for infusions of study treatment and study assessments.

- The last dose of study treatment will be administered at Week 224 (End-of-Treatment Visit). The EOS Visit will occur at Week 226 and the Follow-up Visit at Week 238.
 - Participants who discontinue study treatment prematurely will be asked to remain in the study and continue all protocol-specified visits and procedures. These participants should be encouraged to attend at least the Week 104, 128, 152, 176, 200, and 226 Visits, depending on when treatment was discontinued, and undergo all the scheduled procedures. At a minimum, these visits should include assessment of AEs/SAEs and concomitant medications and key clinical assessments, including at least the CDR, MMSE, ISLT, ADAS-Cog 13, ADCS-ADL, and FAQ. Participants who discontinue study treatment prematurely will also be asked to return to the study site for a Follow-up Safety Visit 14 weeks after receiving the last dose of study treatment.
 - Participants who withdraw from the study prematurely are to return to the study site for an Early Termination Visit and assessments and for the Follow-up Safety Visit 14 weeks after receiving the last dose of study treatment.

Certain visits during the study may be conducted as home visits as specified in the Schedule of Activities, if the Investigator is in agreement and appropriate services are available to perform the required study procedures and adequately monitor for potential safety events.

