5.6.2 Structural MRI Analysis

No subjects reached week 226, the primary analysis timepoint for structural MRI. Therefore, structural MRI is not reported or statistically analyzed for the LTE period.

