	Week 156	1093	[1010, 1261]
	Week 204	1429	[1262, 1506]
	Week 226	1582	≥1507
eCog	Baseline	1	Most recent non-missing pre-dose value
	Week 28	197	[2, 295]
	Week 56	393	[296, 470]
	Week 78	547	[471, the end day of the placebo-controlled period ¹]
	Week 108	757	[one day after the start day of the LTE period ² , 841]
	Week 132	925	[842, 1009]
	Week 156	1093	[1010, 1261]
	Week 204	1429	[1262, 1506]
	Week 226	1582	≥1507
MMSE	Baseline	1	Most recent non-missing pre-dose value
	Week 12	85	[2, 127]
	Week 24	169	[128, 225]
	Week 40	281	[226, 323]
	Week 52	365	[324, 421]
	Week 68	477	[422, 512]
	Week 78	547	[513, the end day of the placebo-controlled period ¹]
	Week 104	729	[one day after the start day of the LTE period ² , 813]
	Week 128	897	[814, 981]
	Week 152	1065	[982, 1149]
	Week 176	1233	[1150, 1317]
	Week 200	1401	[1318, 1492]
	Week 226	1582	≥1493

1 The end day of the placebo-controlled period is the last day on or before the first infusion in LTE for subjects who enter LTE and is the last day in study for subjects who do not enter LTE. 2 The start day of the LTE period is the day of the first infusion in the LTE period.
			

CONFIDENTIAL

The information contained herein may not be used, disclosed, or published without the written consent of Biogen MA Inc.

Table 2. Visit Windows for Laboratory by Visit Summaries using Placebo-Controlled Baseline

Analysis visit	Target visit day	Analysis visit window
Baseline	1	Most recent non-missing pre-dose value
Week 12	85	[2, 127]
Week 24	169	[128, 253]
Week 48	337	[254, 421]
Week 72	505	[422, 526]
Week 78	547	[527, 630* or the end day of the placebo-controlled period ¹]
Week 90*	631	[631, the last day in the study]
Week 100	701	[the start day of the LTE period ² , 785]
Week 124	869	[786, 953]
Week 148	1037	[954, 1121]
Week 172	1205	[1122, 1289]
Week 196	1373	[1290, 1457]
Week 220	1541	[1458, 1562]
Week 226	1582	[1563, 1625]
Week 238	1667	≥1626

* Applicable only for the subjects who do not go to LTE. They are expected to have week 90 follow-up assessment.
 1 The end day of the placebo-controlled period is the last day before the first infusion in LTE for subjects who enter LTE and is the last day in study for subjects who do not enter LTE.
 2 The start day of the LTE period is the day of the first infusion in the LTE period.

Table 3. Visit Windows for Laboratory by Visit Summaries using LTE Baseline

Analysis visit	Target visit day	Analysis visit window	Protocol visit

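### SAP Appendix I places 14-week follow-up results under the wrong visit label: the Week 238 row is set by calendar day although the visit is timed from the last dose, and the LTE-day bounds in Tables 3 and 11 start too late

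*SAP*

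**What the plan says.** **Timing of the visit.** Protocol Table 4 (footnote 3) states: "Participants who discontinue study treatment prematurely are to return to the study site for a Follow-up Safety Visit 14 weeks after receiving the last dose". The column in that table is headed "238/FUV (14 weeks After Last Dose", so it is a Week 238 visit only for someone dosed through Week 224. SAP 2.3 repeats the rule: people who stop early are "asked to return to the study site for a Follow-up Safety Visit 14 weeks after receiving the last dose of study treatment". They are also expected to stay on the visit schedule: "All participants who discontinue study treatment prematurely will be asked to remain in the study and continue all protocol-specified visits and procedures" (Protocol Table 4, footnote 2).

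**Assignment to rows.** SAP Appendix I says that "assessment from all scheduled visits including EOT visit and EOS visit, and all unscheduled visits will be mapped to an appropriate analysis visit", using day windows. Where a window holds several records, none of them from an EOT or EOS visit, "the assessment that is closest to the target visit day will be used for analysis". Nothing in the appendix refers to the last dose or exempts the follow-up visit.

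**Follow-up rows.** With study days counted from the first placebo-controlled dose, the only LTE follow-up row is Week 238. It opens at Day 1626 in Tables 2 (labs), 6 (ECG) and 8 (vital signs), and at Day 1619 in Table 10 (ADA). With days counted from the first LTE dose, the row tagged as protocol Week 238 is ≥1122 in Table 3 (labs), >1163 in Table 11 (ADA) and >1065 in Table 7 (ECG). For people who do not enter the LTE, Tables 2, 6 and 8 carry a Week 90 row with the note "They are expected to have week 90 follow-up assessment".

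**How far people got.** SAP 5.6.2: "No subjects reached week 226, the primary analysis timepoint for structural MRI".

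**The concern.** A reader takes a row headed with a regular visit week as the state of participants at that point in the schedule, and a follow-up row as results 14 weeks after dosing ended. A calendar-day window can honour the second label only if everyone stops at the same time. For anyone who stops early, the follow-up result drifts into whatever row covers that day, and the follow-up row loses it.

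The LTE's primary objective is long-term safety and tolerability, and ADA incidence over time to Week 238 is one of its exploratory endpoints. By-visit safety and ADA rows should therefore contain what their labels say. A second, unrelated slip in Tables 3 and 11 moves even a full-term follow-up into the wrong row.

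**Working it through.** **Inputs.** Nominal day = 7 × week + 1. LTE Day 1 is Study Day 561 (Week 80), so LTE day = study day − 560. Follow-up day = last-dose day + 98. LTE doses run every 4 weeks from Week 80 to Week 224: (224 − 80)/4 + 1 = 37 possible last-dose visits.

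**The SAP's own bounds reproduce.** Week 224 is Day 1569, and 1569 + 98 = 1667, the Week 238 target. The midpoint of 1582 (the SAP's Week 226 target) and 1667 is 1624.5, which matches the 1625/1626 split. For ADA, the midpoint of 1569 and 1667 is 1618, so the row opens at 1619. These bounds suit a completer.

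**Defect 1: early stoppers.** Reaching the Week 238 row needs a last dose on Day 1626 − 98 = 1528 or later (ADA: 1619 − 98 = 1521). On the dosing grid:
- last dose Week 220 (Day 1541): follow-up Day 1639, in the Week 238 row;
- last dose Week 216 (Day 1513): follow-up Day 1611, not in it.

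Moving the follow-up by ±7 days gives 1632–1646 and 1604–1618, so the split stands. Hence 2 of 37 last-dose visits reach the row and 35 (Weeks 80–216) do not. Those 35 map as follows:

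| Table | Regular visit row | Week 226/EOS row |
|---|---|---|
| 2, labs | 33 (last dose to Week 208) | 2 (Weeks 212, 216) |
| 6, ECG | 30 (to Week 196) | 5 (Weeks 200–216) |
| 8, vital signs | 33 (to Week 208) | 2 (Days 1583 and 1611, in [1577, 1625]) |
| 10, ADA | 35 (Week 216 goes to Week 224) | no such row |

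Example: last dose Week 100 (Day 701), follow-up Day 799. Labs go to Week 124 ([786, 953]), ECG to Week 104 (up to 813), ADA to Week 116 ([772, 953]).

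**Which record is used.** If the same person stays and attends Week 124 on Day 869, that lab is 0 days from target and the follow-up is 869 − 799 = 70 days away, so the follow-up is dropped. With every visit attended on its nominal day, the follow-up is selected for 0 of 35 last-dose visits in Tables 2, 6 and 10. If the person withdraws and any ET visit is ignored, it is selected for 35 of 35 (labs), 35 of 35 (ECG) and 32 of 35 (ADA; the exceptions are Weeks 116, 120 and 196). The rule does not say how EOT, EOS or ET records compete, so results in rows that contain such records are less certain.

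**Defect 2: LTE-day bounds.** A full-term follow-up is LTE Day 1667 − 560 = 1107.
- Table 7 (ECG): 1107 > 1065, correct row.
- Table 3 (labs): 1107 lies in [954, 1121], the row for protocol Weeks 220 and 226. Its own row starts at 1122.
- Table 11 (ADA): 1107 lies in [954, 1163], the row for protocol Week 224. Its own row starts at 1164.

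No last-dose visit reaches the follow-up row in Table 3 or Table 11 (0 of 37), because the latest possible follow-up is LTE Day 1107. Other Table 11 bounds are off too: protocol Week 116 is LTE Day 813 − 560 = 253, which falls in [2, 253], the row for protocol Week 104.

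Midpoints in LTE days would be (1023 + 1107)/2 = 1065 for labs, opening the follow-up row at 1066 as Table 7 does, and (1009 + 1107)/2 = 1058 for ADA, opening it at 1059.

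**The case against.** **Stoppers stay on schedule.** This is the strongest reply, and it stands. The closest-to-target rule then reports the regular visit, so it would be wrong to infer that every early stopper's follow-up is shown as a treatment-visit result. Where a record maps and whether it is reported are separate questions. A withdrawer's ET visit can also supply labs and ECG.

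**Regular rows are not purely on-drug anyway.** Also true. Someone last dosed at Week 100 who attends Week 124 gives a lab 869 − 701 = 168 days off drug, by design. The defect is one of visit labelling, and correcting it does not produce on-drug rows.

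**Late stoppers.** Some of their results fall in the Week 226/EOS row, which is already post-treatment. There the mismatch is 14 weeks after the last dose against a nominal 2.

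**Intent.** The SAP does not always separate follow-up results: Table 10 has no Week 90 row although Protocol Table 1 schedules an ADA sample then. This weakens any argument from intent but leaves the Week 238 rows defined in a way that does not match the visit.

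**Size.** A reader might infer that on-drug shifts are diluted toward baseline. The documents give no half-life, no expected lab or ECG shift and no LTE numbers by visit, so that is conjecture. The 2 of 37 counts possible stopping visits, not participants.

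**Tables 3 and 11.** Their failure has nothing to do with last-dose timing, and it is not shared by every LTE-baseline table: Table 7 (ECG) and Table 9 (vital signs, from 1052) both place the full-term visit correctly. It has to be treated as a separate error.

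**Conclusion.** Both defects hold, with limited reach.

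1. On nominal timing, an LTE participant last dosed at Week 216 or earlier has the follow-up visit mapped outside the Week 238 row in Tables 2, 6, 8 and 10. The result is actually reported under the other label mainly for people who withdraw or miss visits. If the statement in SAP 5.6.2 that nobody reached Week 226 holds for attendance generally, the Week 238 rows would be empty. That section speaks about structural MRI, so this remains conditional.
2. Tables 3 and 11 place even a full-term follow-up one row early. Table 3 matters because SAP 5.4.3.1 uses the LTE baseline for late-start lab changes. Whether Table 11 is used is uncertain, because SAP 5.7.1 defines the ADA baseline from the placebo-controlled period.

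Only descriptive by-visit lab, ECG, vital-sign and ADA summaries and plots are touched. AE tables, lab shift tables, potentially clinically significant abnormality counts and CDR-SB are unaffected; the qualitative lab analyses use all values, not the windowed record. The size of the effect cannot be worked out from the documents. The arithmetic assumes doses on nominal days, LTE Day 1 at Study Day 561 and follow-up at +98 days. The correction is cheap and worth making, but no main conclusion depends on it.

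**What to change.** - **Give the follow-up visit its own row.** Before calendar windowing, assign every record carrying the CRF Follow-up Safety Visit label to a row titled Follow-up (14 weeks after last dose), and exclude those records from all other rows. Apply this to labs, ECG, vital signs and ADA, under both the placebo-controlled and the LTE baseline.
- **Do not use a days-since-last-dose cutoff.** A cutoff of 70 days, for example, would relabel every later scheduled visit of a person who stops treatment but stays in the study, such as the Week 124 visit 168 days after a Week 100 last dose.
- **Recompute the Table 3 and Table 11 targets and bounds in LTE days.** Midpoint bounds would open the follow-up row at LTE Day 1066 for labs and 1059 for ADA. On its own this helps completers only.
- **Add a footnote** that regular visits attended after stopping treatment stay in their scheduled rows, so those rows are not purely on-drug.

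The cost is a few lines of SAP text and one derived flag, with no new data. Some late LTE rows will show a smaller n.
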